
 • Bleeding adverse events are considered an important identified risk for M7824. • In general, mild and moderate mucosal bleedings resolve without discontinuation of treatment. • These events may include, but are not limited to the following: 
 ○ Epistaxis ○ Hemoptysis ○ Gingival bleeding ○ Hematuria 	
Non-tumor Bleeding	
Grading	Management
Grade 2	
 • If resolves to Grade ≤ 1 by the day before the next infusion, study intervention may be continued. • If not resolved to Grade ≤ 1 by the day before the next infusion, but is manageable and /or not clinically relevant, consult Medical Monitor to assess if clinically reasonable to administer the following infusion.
Grade 3	
 • Permanently discontinue treatment unless an alternative explanation can be identified (such as concomitant use of antithrombotic agents, traumatic events, etc.) • In case of alternative explanations, hold study treatment until the event recovers to Grade ≤ 1

Grade 4	
 Treatment must be permanently discontinued if no alternative explanation is identified.
Tumor Bleeding	
Grade \geq 2	
 Study treatment must be held till the event recovers to Grade \leq 1 Permanently discontinue treatment if the Investigator considers the participant to be at risk for additional severe bleeding.

Table 12: Impaired Wound Healing

 Impaired wound healing is considered important potential risk for M7824 Management should be discussed with Medical Monitor for participants requiring surgery on study. It is recommended to hold study intervention for approximately 4 weeks post major surgery for observation. Post-operative wound healing should be closely monitored

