¹⁴ A Safety Follow-up visit is scheduled 4 weeks (28 ± 5 days) after the last administration of M7824 or M9241 but before any new therapy is started, if possible, whichever occurs earlier. All SAEs ongoing at the 28-Day Safety Follow-up visit must be monitored and followed up by the Investigator until stabilization or until the outcome is known, unless the subject is documented as “lost to follow-up.” In addition, all trial drug-related SAEs occurring after 28 Day Safety Follow up visit and ongoing at the Safety Follow-up visit have to be followed up in the same manner

¹⁵ Subjects with PD will be followed every 12 weeks (± 2 weeks) by phone or e-mail for survival and further tumor therapy for 1 year after the last dose of study drug. After 1-year subjects will be followed for survival every 6 month. Subjects without progressive disease at 28-Day Safety Follow-up visit will be invited to Clinical Center to perform CT scans (or MRI scans if clinically indicated) every 12 weeks (± 2 weeks) until PD. Outside scans are acceptable.

¹⁶ If subjects are not willing to come to NIH after treatment discontinuation for FU visits, they will be followed by phone call or e-mail.

¹⁷ Must be done before re-treatment after surgery.

¹⁸ Every 6 weeks

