3.11.2 Off -Study Criteria

- Death

- Patient request to be withdrawn from study
- Lost to follow up
- PI discretion
- PI decision to end the study

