10.1.2 Secondary endpoints

- Overall survival in patients after completion of SBRT in combination with M9241 and M7824.
- Progression-free survival of all patients and PFS of patients who did not undergo surgical resection (expressed as median PFS).
- Fraction of patients with LAPC who can undergo surgical resection after M7824 and M9241 in combination with SBRT treatment.
- Time-to-recurrence in patients who underwent surgical resection will be measured as time from surgical resection to disease recurrence (expressed in months).
- Rate of complete pathologic response will be measured as fraction of patients who had a complete pathologic response of all patients who underwent surgery.

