10.4.3 Analysis of the secondary endpoints

The secondary endpoints will be analyzed as follows:

- Overall survival in patients after completion of SBRT in combination with M9241 and M7824 and Progression-Free Survival (PFS) of all patients and PFS of patients who did not undergo surgical resection (expressed as median PFS). Overall survival and PFS will be determined in all patients treated at the MTD of M7824 and M9241 in combination with SBRT, as well as patients who did not undergo surgery, using Kaplan-Meier curves.
- Fraction of patients with LAPC who are able to undergo surgical resection after M7824 and M9241 in combination with SBRT treatment. This will be reported along with a 95% confidence interval on the fraction.

- Time-to-recurrence in patients who underwent surgical resection will be measured as time from surgical resection to disease recurrence (expressed in months). Time-to-recurrence in patients will be calculated via Kaplan-Meier curves. Any comparisons with published results will be interpreted as being exploratory.
- Rate of complete pathologic response will be measured as fraction of patients who had a complete pathologic response of all patients who underwent surgery. This will be reported along with a 95% confidence interval.

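### Time-to-recurrence after resection has recurrence as its only event and is estimated by Kaplan-Meier, so if any patient dies without recurrence the curve overstates the proportion who recur

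*Combined protocol and SAP*

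**What the plan says.** Section 10.1.2 defines the endpoint: "Time-to-recurrence in patients who underwent surgical resection will be measured as time from surgical resection to disease recurrence (expressed in months". Section 10.4.3 repeats that definition and names one estimator: "Time-to-recurrence in patients will be calculated via Kaplan-Meier curves". It adds that "Any comparisons with published results will be interpreted as being exploratory".

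Neither section mentions death for this endpoint, gives a censoring rule, or names a competing-risk method. Death is an off-study criterion in section 3.11.2, so observation for recurrence ends there.

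For the other time-to-event endpoints, 10.4.3 plans overall survival and PFS for all patients treated at the MTD with SBRT and for patients who did not have surgery. Neither is planned for resected patients as a group. A median is promised for PFS ("PFS of patients who did not undergo surgical resection (expressed as median PFS"), whereas time-to-recurrence is only to be expressed in months.

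**The concern.** Kaplan-Meier treats a censored patient as someone who could still have the event later, at the same rate as those still followed. A patient who has died cannot recur. If death without recurrence is a censored time, the curve describes recurrence in a setting where such deaths have been removed. One minus the curve is then larger than the proportion of resected patients who actually recur.

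The other natural reading, time alive and free of disease after surgery, errs in the opposite direction. A patient who dies in the first post-operative month leaves the risk set without lowering the curve, so a median read as disease-free time is too long. The same figure therefore looks too pessimistic as a recurrence probability and too favourable as a disease-free time.

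Death without recurrence is foreseeable here. The regimen is described as neoadjuvant / perioperative. Section 3.4.1 says "Impaired wound healing is considered important potential risk for M7824" (Table 12), and Table 11 classes bleeding as an identified risk. Section 1.2.7 reports late grade 3 GI bleeding after SBRT. Section 10.4.3 also anticipates that the result may be set beside published series, and such a comparison depends on how each side counted deaths.

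**Working it through.** **Plan's own figure.** There is none for this endpoint: no recurrence rate, death rate, sample size or precision. The rates below are assumptions.

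**How many patients.** Phase II has 25 evaluable patients (10.2). Section 1.2.1 gives resection rates of 40–60% for borderline resectable and 7–19% for unresectable disease.

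- 25 × 0.40 to 25 × 0.60 = 10 to 15 patients
- 25 × 0.07 to 25 × 0.19 = 1.75 to 4.75, about 2 to 5 patients

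The subset is therefore roughly 2 to 15 patients.

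**Formulas.** Take constant hazards, r for recurrence and d for death without recurrence, and let L = r + d.

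- One minus Kaplan-Meier with deaths censored: 1 − exp(−r·t)
- Cumulative incidence of recurrence: (r/L)·(1 − exp(−L·t))
- Median recurrence-free survival: ln 2 / L
- Share of first events that are deaths without recurrence: d/L

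**Main scenario.** Kaplan-Meier median 15 months, so r = ln 2/15 = 0.0462 per month, with t = 24 months. One minus Kaplan-Meier is 1 − exp(−0.0462 × 24) = 67.0% in every row. At a 20% share, L = 0.0462/0.8 = 0.0578 and the cumulative incidence is 0.8 × (1 − exp(−0.0578 × 24)) = 0.8 × 0.75 = 60.0%.

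| Deaths as share of first events | 1 − KM | Cumulative incidence | Overstatement (points) | Median recurrence-free survival (months) |
|---|---|---|---|---|
| 0% | 67.0% | 67.0% | 0 | 15.0 |
| 5% | 67.0% | 65.4% | 1.6 | 14.2 |
| 10% | 67.0% | 63.8% | 3.2 | 13.5 |
| 20% | 67.0% | 60.0% | 7.0 | 12.0 |
| 30% | 67.0% | 55.6% | 11.4 | 10.5 |

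**Sensitivity to the assumed median.**

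- 10 months: 1 − KM is 81.1%, against 78.5 / 75.8 / 70.0 / 63.5% for shares of 5 / 10 / 20 / 30%. The overstatement is about 3, 5, 11 and 18 points.
- 20 months: 1 − KM is 56.5%, against 55.4 / 54.3 / 51.7 / 48.7%. The overstatement is about 1, 2, 5 and 8 points.

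**Second set of hazards.** With r = 0.06 and d = 0.005 / 0.01 / 0.02 per month, the shares are 7.7 / 14.3 / 25% of first events. At 24 months 1 − KM is 76.3%, against 72.9 / 69.7 / 64.0%, a gap of 3.4 / 6.6 / 12.3 points. The Kaplan-Meier median is 11.6 months, against 10.7 / 9.9 / 8.7 months alive and free of recurrence.

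**Small-sample illustration.** Ten resected patients have first events at months 2, 4, 6, …, 20. Those at months 2 and 10 are deaths without recurrence; the rest are recurrences. By month 14 Kaplan-Meier gives (8/9)(7/8)(6/7)(4/5)(3/4) = 0.40, so 1 − KM = 60%, while 5 of 10 patients (50%) have recurred. At month 20 the figures are 100% and 80%. With only the month-2 death, they are 100% and 90% at month 20.

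**The case against.** The strongest reply is that this is an omission in a minor endpoint. The text never says that deaths are censored. If nobody dies before recurring, nothing is wrong. The endpoint is secondary and descriptive, no alpha, sample size or go/no-go rule depends on it, and comparisons with published results are already labelled exploratory. Sampling error in so few patients exceeds the bias: with 15 patients and 67% recurrence, ignoring censoring, the standard error is √(0.67 × 0.33/15) = 0.12, or 12 points.

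Most of that stands and limits the weight of the point. It does not remove it. With recurrence as the only event and Kaplan-Meier as the only estimator, the definition leaves a death without recurrence nowhere to go except a censored time. Sampling error can be shown with an interval; a bias from the choice of estimand cannot. An exploratory label on a comparison does not settle what is being compared.

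A reader might infer three stronger things that the documents do not support.

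- **That the curve and its median are simply wrong.** The error is conditional on deaths without recurrence, and the plan does not promise a median for this endpoint.
- **That the plan hides perioperative deaths.** Overall survival covers all patients treated at the MTD with SBRT, including resected ones. Death is an SAE criterion (8.1.2). Deaths within 30 days of a research intervention, unless due to progression, go to the Clinical Director (7.3). One attributable grade 5 event within 28 days of an agent halts enrolment (3.2).
- **That a Kaplan-Meier curve censoring deaths must be dropped.** It still describes recurrence with death removed and can be shown if labelled that way.

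The documents also give no perioperative death rate, and section 1.2.1 names undetected micrometastasis as the commonest cause of death in this disease. Many deaths may therefore follow recurrence, which points towards the lower shares in the table without excluding the higher ones.

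**Conclusion.** The point holds in conditional form. As defined, the analysis can treat a death without recurrence only as censored; if any occur, one minus the curve overstates the proportion who recur, and the curve is not a disease-free time. The size rests on assumed constant hazards. For a 15-month median it runs from zero with no such deaths, through about 2 to 3 points at 5–10% of first events, to 7 to 11 points at 20–30%. A faster recurrence rate makes the gap larger and a slower one makes it smaller. In a subset of roughly 2 to 15 patients a single such death can move the curve visibly.

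It is worth correcting despite the endpoint's modest role, because time-to-recurrence is the only time-to-event summary planned for the resected group alone and it does not count these deaths as failures. It does not affect the primary analysis or any decision rule.

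**What to change.** In 10.1.2 and 10.4.3:

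1. Add recurrence-free survival from the date of resection, with recurrence or death from any cause as the event, estimated by Kaplan-Meier, and state the censoring rule for patients alive without recurrence.
2. For recurrence alone, report the cumulative incidence of recurrence with death without recurrence as a competing event (Aalen-Johansen estimator).
3. If a Kaplan-Meier curve that censors deaths is kept, label it as such and do not report one minus the curve as the probability of recurrence.

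The cost is a few lines of SAP text and one extra analysis. The planned follow-up should already supply the dates: section 3.8 says "Subjects without progressive disease at 28-Day Safety Follow-up visit will be invited to Clinical Center to perform CT scans", at 12-week intervals until progression, and overall survival is itself an endpoint. The downside is that the reported median may be shorter once deaths count as events. Settling this before the data are seen also avoids a post-hoc choice in a very small group.

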10.4.4 Safety analyses

Patients in the phase I portion of the trial will be assessed for toxicity by reporting the grades of toxicity and the type of toxicity observed for all patients. Patients will be enrolled and evaluated in the phase I cohorts of the trial as described in the phase I sample size determination section. Patients will continue to be enrolled onto the phase II cohort if the cumulative fraction of patients with greater or equal grade 3 DLT is less than 1/3.

10.4.5 Baseline descriptive statistics

Limited demographic and clinical characteristics of all patients will be reported, for both the phase I and the phase II cohorts.

10.4.6 Planned interim analyses:

Toxicity will be assessed within each group of 6 patients accrued in the phase I cohorts M7824 in combination with M9241, and M7824 and M9241 in combination with SBRT. The fraction of patients who respond in the phase IB part who received M7824 and M9241 in combination with SBRT will be included into the efficacy assessment of the phase II cohort, as indicated in the phase II sample size determination section.

10.4.7 Exploratory analyses

The following are the exploratory objectives, along with the method of analysis of each:

- To determine M7824 PKs. This will be done using descriptive measures only.
- To determine ADA profile of M7824 in combination with M9241. This will be done using descriptive measures only.
- To evaluate serum cytokines and tumor necrosis factor (TNF) levels pre-treatment and on-treatment. These measures will be evaluated using descriptive statistics. Comparisons between pre-treatment and on-treatment levels may be done using a paired test such as a Wilcoxon signed rank test.
- To correlate the tumoral immune infiltrate via IHC with clinical outcome, the levels will be compared between responders and non-responders using an exact Wilcoxon rank sum test.
- To evaluate impact of genomic profile of advanced pancreatic cancers on clinical response to M7824 and M9241 in combination with SBRT. The prevalence of common somatic mutations identified within the 50-cancer gene panel (Molecular Pathology; [name]; for example, KRAS, TP53, SMAD/TGBR2, CDKN2A) obtained from each patient will be compared between responders and non-responders. This will be done using

either a Fisher's exact test, Cochran-Armitage trend test, or exact Wilcoxon rank sum test depending on the distributions of values.

- To correlate circulating free tumor DNA (ctDNA) levels with clinical course of pancreatic cancer patients treated with M7824 and M9241 in combination with SBRT. The levels will be compared between responders and non-responders using an exact Wilcoxon rank sum test.
- To measure subjective Health-related Quality of Life (HRQoL) affecting disease-specific symptoms and treatment-related concerns pre-treatment and on-study and compare HRQoL scores with historical controls of other QoL interventions in advanced pancreas cancer patients. Health-related Quality of Life (HRQoL) scores measuring patient-reported disease-specific symptoms and treatment-related concerns will be compared between responders and non-responders using an exact Wilcoxon rank sum test. The results will also be compared informally with historical controls of other QoL interventions in advanced pancreas cancer patients, using descriptive methods.
- To evaluate the impact of M7824 in combination with M9241 on tumoral perfusion measured by perfusion-weight Dynamic Contrast-enhanced (DCE) Magnetic Resonance Imaging (DCE-MRI). This will be done using descriptive statistics.

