1 INTRODUCTION

1.1 STUDY OBJECTIVES:

1.1.1 Primary Objectives:

- To determine the safety and tolerability and the recommended phase 2 dose (RP2D) of M7824 and M9241 in combination with SBRT as neoadjuvant / perioperative treatment in subjects with pancreas cancer.
- To determine a preliminary estimate of efficacy as best overall response (BOR) according to RECIST 1.1 of M7824 and M9241 in combination with SBRT as neoadjuvant / perioperative treatment in subjects with locally advanced pancreas cancer.

1.1.2 Secondary Objectives:

- To assess overall survival (OS) in patients after completion of RT in combination with M9241 and M7824.
- To assess progression-free survival (PFS) for all participants.
- To assess progression-free survival (PFS) for participants who did not undergo surgical resection.
- To determine fraction of patients with LAPC who are able to undergo surgical resection after M7824 and M9241 in combination with SBRT treatment.
- For patients who underwent surgical resection after M7824 and M9241 in combination with SBRT treatment:
 - To determine time-to-recurrence of the disease
 - To determine complete pathological response rate(s)

1.1.3 Exploratory Objectives:

- To determine ADA profile of M7824 in combination with M9241.

- To determine the PK of M7824 in combination with M9241.
- To evaluate serum cytokines and tumor necrosis factor (TNF) levels pre-treatment and on-treatment.
- To correlate the tumoral immune infiltrate via IHC with clinical outcome.
- To evaluate impact of genomic profile of advanced pancreatic cancers on clinical response to M7824 and M9241 in combination with SBRT.
- To correlate circulating free tumor DNA (ctDNA) levels with clinical course of pancreatic cancer patients treated with M7824 and M9241 in combination with SBRT.
- To measure subjective Health-related Quality of Life (HRQoL) affecting disease-specific symptoms and treatment-related concerns pre-treatment and on-study and compare HRQoL scores with historical controls of other Quality of Life (QoL) interventions in advanced pancreas cancer patients.
- To evaluate the impact of M7824 in combination with M9241 on tumoral perfusion measured by perfusion-weight Dynamic Contrast-enhanced (DCE) Magnetic Resonance Imaging (DCE-MRI).

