5.1.2 Tumor and Tissue Collection

Archival tumor samples (collected within 6 months prior to treatment) might be collected at baseline and from the surgical specimen when patients undergo resection.

Test/assay	Volume (approx.)	Type of tube*	Collection point	Location of specimen analysis (and original processing)
PK M7824	Blood, 4 mL	SST	See section 5.1.3	EMD Serono (BPC)
ADA by ELISA	Blood, 4 mL	SST	See Study calendar 3.8	EMD Serono (BPC)
Cytokines by ELISA	Blood, 8 mL	SST	See Study calendar 3.8	EMD Serono (BPC)
TNF by ELISA	Blood, 2x3 mL	Light blue citrate	See Study calendar 3.8	EMD Serono (BPC)
Immune marker panel evaluation by IHC	Archival tumor sample and		Baseline and at surgery	Laboratory of Pathology, NCI

Test/assay	Volume (approx.)	Type of tube*	Collection point	Location of specimen analysis (and original processing)
	surgery sample			
161 DNA-target panel (Oncomine v3 Comprehensive Assay v3)	Archival tumor sample or surgery sample		Baseline or at surgery	[name], Laboratory of Pathology NCI
Circulating free tumor DNA (ctDNA)	Blood, 6 mL	EDTA (purple top) tubes	See Study calendar 3.8	[name], Laboratory of Pathology NCI (BPC)

* Tubes/media may be adjusted at the time of collection based upon materials available and/or to ensure the best viable samples are collected for planned routine and/or research analysis at the time of procedure.

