5.2 SAMPLES FOR GENETIC/GENOMIC ANALYSIS

5.2.1 Description of the scope of genetic/genomic analysis

5.2.1.1 Somatic genomic profile of pancreatic cancers derived from specimens

There is clinical evidence that mutation load drives outcome of immunotherapy in pancreas cancer, and emerging evidence that certain neo-epitopes derived from somatic mutations are more immunogenic than others. For example, it has been postulated that mutations in chromatin-remodeling genes, present in up to 17% of pancreas cancer specimens, or variants affecting the TGF β receptor - SMAD axis, are positively associated with outcome to immunotherapy in cancer. Thus, early correlations between genotype and clinical outcome of patients aim to (1) improve future selection of patients for the dual TGF β ‘trap’ PD-L1 blockade and M9241 immunocytokine therapy in combination with RT approach as well as (2) improve understanding of the mechanism of action of these agents in pancreas cancer which would aid design of future combination therapies.

We will use baseline archival samples as available for somatic tumor variant sequencing which will be performed by the CLIA-approved 50-cancer gene panel of the Molecular Pathology section ([name] lab).

5.2.2 Circulating free tumor DNA measures:

Measures of copies of genomic tumor DNA released into the circulation has been shown to be an accurate measure of tumor burden in patients with solid organ cancers and to have value to follow response to anti-cancer treatment both for the early identification of responders as well as patients

to recur after remission. Including longitudinal measurements from baseline and on-treatment of circulating free tumor DNA into explorative objectives examines the value of identifying responders early and the development of this test as a predictive biomarker for the tested M7824 M9241 combination treatments with SBRT.

We plan to characterize cfDNA from blood before and during treatment. All samples will be subjected to targeted sequencing. This will allow us to characterize somatic point mutations, and copy-number changes and will be performed in [name]'s laboratory.

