Following determination of safe doses of M7824 and M9241 when combined with SBRT the study may proceed to the phase II part. Thus, a minimum of 12 and a maximum of 24 evaluable patients will be enrolled in the phase I cohorts.

Phase II:

The study will be conducted using a Simon two-stage phase 2 minimax design. The objective of the trial will be to determine whether this novel combination of M7824 and M9241 in combination with SBRT can be associated with a response rate (PR + CR; RECIST) that can rule out 10% ($p_0=0.10$) in favor of an improved response rate of 30% ($p_1=0.30$). Using $\alpha=0.10$ (probability of accepting a poor agent) and $\beta=0.10$ (probability of rejecting a good agent), initially 16 evaluable patients will be enrolled into the phase II study, including up to 6 patients from the completed safety cohort Phase IB of M7824 and M9241 in combination with SBRT if they are completely eligible for the phase II portion of the trial. If 0 to 1 of 16 patients respond, then no further patients will be enrolled. If 2 or more of the first 16 evaluable patients enrolled have a response (PR or CR), then accrual will continue until a total of 25 evaluable patients have been enrolled. If 2 to 4 of the 25 has a clinical response, then this will be considered inadequate for further investigation of this regimen. If 5 or more of 25 (20%) respond, then this will warrant further investigation in a subsequent trial. Under the null hypothesis (10% response rate), the probability of early termination is 51.5%.

Thus, with up to 24 participants in the phase I cohort and up to 25 evaluable participants in phase II, the trial may require up to 49 participants to be treated. This number may be reduced by up to 6 patients if there are < 2 DLTs in the second safety run-in of M7824 and M9241 in combination with SBRT and those patients are included in phase II. To allow for a small number of inevaluable

patients, the accrual ceiling will be set at 52 participants. With an anticipated accrual rate of 10 patients per year, it is expected that the trial may complete accrual within 5 years.

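### The IHC and ctDNA association analyses use only a responder split, which cannot reach p = 0.05 after a Stage 1 stop and keeps roughly half the power at about 5 of 25 responders; separately, the genomic panel and tissue source are contradictory

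*Combined protocol and SAP*

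**What the plan says.** For the immune infiltrate, section 10.4.7 states: "To correlate the tumoral immune infiltrate via IHC with clinical outcome, the levels will be compared between responders and non-responders", by an exact Wilcoxon rank sum test. The ctDNA objective in section 1.1.3 begins "To correlate circulating free tumor DNA (ctDNA) levels with clinical course of pancreatic cancer patients", and section 10.4.7 again compares levels between responders and non-responders with the same test. HRQoL scores get that test too, plus an informal comparison with historical controls. The genomic objective is clinical response itself; mutation prevalence is compared by responder status with Fisher, Cochran-Armitage or exact Wilcoxon tests. Section 10.4.7 states no significance level, no analysis set, no continuous or time-to-event outcome for these associations, and no rule for 0 or 1 responders.

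Section 10.2 stops Phase II if 0 or 1 of the first 16 patients respond, otherwise continues to 25, and counts 5 or more responders as success. It says "Under the null hypothesis (10% response rate), the probability of early termination is 51.5" percent.

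On the genomic input, the table in section 5.1.2 lists a "161 DNA-target panel (Oncomine v3 Comprehensive Assay v3") on an archival or a surgery sample, taken at baseline or at surgery. Section 5.2.1.1 says "We will use baseline archival samples as available for somatic tumor variant sequencing", using a 50-gene panel. Section 10.4.7 also names the 50-gene panel.

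**The concern.** For IHC and ctDNA, the planned test is narrower than the objective. Outcome is reduced to one yes/no variable that the design expects to be rare, while tumor size is measured on a continuous scale. Two things are at stake. If the regimen looks inactive and Stage 1 stops, the marker work may yield no usable test just when it could help explain the failure. If the regimen goes on, information already collected is discarded.

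The genomic problem is different. Surgery tissue is post-treatment and exists only in patients who reach surgery. If it stands in for baseline tissue in some patients, treatment-induced change and selection for surgery can enter the genotype-response comparison. Two panels of different content would add a further difference between patients.

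**Working it through.** **1. Reproduce the plan's figure.** Inputs from section 10.2: 16 patients in Stage 1, stop at 0 or 1 responders, null rate 10%. P(stop) = 0.9^16 + 16 × 0.1 × 0.9^15 = 0.1853 + 0.3294 = 0.5147, which matches the stated 51.5%. The same formula at other true rates:

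| True rate | P(0 responders) | P(1 responder) | P(stop) |
|---|---|---|---|
| 10% | 18.5% | 32.9% | 51.5% |
| 20% | 2.8% | 11.3% | 14.1% |
| 30% (design target) | 0.3% | 2.3% | 2.6% |

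**2. What the split can show after a stop.** With 0 responders there is nothing to compare. With 1 against 15, the single responder's rank takes 16 equally likely values, so the smallest two-sided exact Wilcoxon p is 2/16 = 0.125. The smallest Fisher p is 1/16 = 0.0625. Neither can reach 0.05.

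**3. Power if the trial continues.** The documents give no correlation and no significance level. Assumed here: marker and tumor change bivariate normal, n = 25, two-sided 0.05, responders being the patients with the best tumor change; 20,000 simulated trials.

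| Correlation | Spearman on continuous change | Split, 5 responders | Split, 7 responders |
|---|---|---|---|
| 0.3 | 28% | 14% (50% kept) | 17% (61% kept) |
| 0.4 | 47% | 23% (48% kept) | 28% (60% kept) |
| 0.5 | 68% | 36% (53% kept) | 43% (64% kept) |

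At a correlation of 0.5 the split has about 20% power with 2 responders and 27% with 3, that is 20/68 = 29% and 27/68 = 40% of the Spearman power. At 0.7 with 5 responders it keeps 73% (71% against 97%). Given continuation, the mean number of responders in 25 is 3.5, 5.4 and 7.6 at true rates of 10%, 20% and 30%.

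A cross-check without simulation is the asymptotic efficiency of cutting a normal outcome at its top fraction q, φ(z)²/(q(1−q)). It is 0.34, 0.49 and 0.58 at q = 0.10, 0.20 and 0.30, so about half the information remains at 20% responders.

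**4. What a continuous outcome offers after a stop.** With n = 16, given a stop at a 10% rate, Spearman power is 26%, 41%, 59% and 78% at correlations of 0.4, 0.5, 0.6 and 0.7. This is modest, but the analysis exists.

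**5. Are the data there?** Measurable disease is an entry criterion (2.1.1). Section 6.3.1 records the baseline sum of diameters as the reference for regression. Scans start at Cycle 3 Day 15 (6.3). The Study Calendar (3.8) has ctDNA at baseline and on Day 1 of cycles, so Cycle 2 Day 1 precedes the first response scan. Archival tissue is collected only if available, so the real n for IHC is below 25 and both methods lose power.

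**6. Genomic input, side by side.**

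| Section | Panel | Tissue |
|---|---|---|
| 5.1.2 | 161 targets | archival or surgery |
| 5.2.1.1 | 50 genes | baseline archival |
| 10.4.7 | 50 genes | not stated |

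These cannot all be followed.

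**The case against.** The split answers questions that the protocol does ask. Section 5.1.6 looks for an immune footprint associated with response, section 5.2.2 wants ctDNA to identify responders early, and response is the primary efficacy endpoint. This stands, so the responder comparison should be kept and the continuous outcome added to it.

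Section 10.4.7 names no analysis set, and the IHC item is not limited to patients given SBRT. Cohort 1 has 6 to 12 patients. If 6 of them were pooled at the same assumed 10% rate, then after a stop the chance of at least 2 responders in 22 is (0.1853 × 0.1143 + 0.3294 × 0.4686)/0.5147 = 34%, and the smallest p becomes 2/231 = 0.009. This stands for IHC only, because the ctDNA and genomic objectives are tied to SBRT.

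Diameter change has its own weakness. Section 1.2.1 concedes that imaging cannot reliably separate tumor from fibrous tissue, and the main target lesion is the irradiated primary. The simulated advantage may therefore be optimistic.

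Finally, these are exploratory analyses with no stated significance level. After a stop the data can still be shown descriptively; what is lost is the test.

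**Conclusion.** The point holds for IHC and ctDNA, at minor to moderate severity. After a Stage 1 stop, a responder test limited to the 16 patients is either undefined or bounded below by p = 0.125. With continuation and about 5 of 25 responders, the split keeps roughly half the power of a continuous outcome at correlations of 0.3 to 0.5, less with 2 or 3 responders, and about 60 to 65% with 7. These power figures rest on an assumed correlation, bivariate normality, a 0.05 level and complete data. HRQoL shares the split and its limits. The panel and tissue contradiction needs no assumption; the resulting bias is possible but not demonstrated, since resection is not the same as RECIST response.

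Three stronger readings are not supported. A reader might take 51.5% as the general chance of an unusable split, but it applies only at a true rate of 10%. A reader might infer that power is always halved, but the loss varies with responder count and correlation. A reader might also think the genomic analysis suffers most from the split. Its objective is clinical response, so the split fits it. In simulations with 3 to 12 mutation carriers, 5 or 7 responders and effects of 0.8 to 2.0 SD, Fisher's test kept between 31% and about all of the power of a Wilcoxon test on continuous change. The genomic defect lies in the input.

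**What to change.** In section 10.4.7:

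- **IHC and ctDNA:** add best percent change from baseline in the sum of target diameters as the main association outcome, by Spearman correlation with a 95% confidence interval. Include a sensitivity analysis for patients without a post-baseline scan, and use PFS and OS as supportive outcomes.
- **ctDNA time points:** use the baseline level and the change to Cycle 2 Day 1.
- **Responder comparisons:** keep them, but as descriptive only when there are fewer than 2 responders. State the analysis set, including whether Cohort 1 enters the IHC analysis.
- **Genomics:** keep clinical response as the outcome. Reconcile sections 5.1.2, 5.2.1.1 and 10.4.7 to one named panel, and use pre-treatment tissue only for this comparison.

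The cost is protocol and SAP wording plus some analysis work; no new samples or scans are needed. There are two downsides: diameter change is noisy in an irradiated, fibrotic primary, and leaving out patients with only a surgery sample slightly lowers the genomic n.
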